9.4. DTX301 Vector Genome Determination and Viral Shedding

Saliva, stool, and urine samples will be collected at scheduled time points for viral shedding, while blood samples will be collected at scheduled time points for vector genome determination. The presence of DTX301 will be determined by [REDACTED]. A summary table will be presented by sample type and DTX301 dose/prophylactic corticosteroids in the SS. Observed results and change from baseline to each scheduled post-baseline time point will be presented. Observed results will also be presented over time by sample type in a figure for each subject. Relevant individual vector shedding data (baseline value, highest value/timepoint, timepoint where the 3rd consecutive low value after peak) will be provided for each patient and sample type. Median values over time by cohort and sample type will be presented in a figure. Longitudinal displays of individuals data over time by cohort for each sample type will be presented.

Following protocol amendment 5, the assessment of vector genome determination was removed globally and viral shedding sampling was reduced based on medical consideration of results to date and to reduce subject burden.

The planned outputs for vector genome determination will be still created, but patients enrolled under protocol amendment 5 or a subsequent protocol amendment will not be included.

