3.2.3.1 Home or Clinic Visits

Subjects will be asked to provide clinical laboratory samples approximately every 4 days through Week 12 of the study. Through Week 12, one sample for spot ammonia will be collected

Protocol: 301OTC01

approximately once a week, and sent to the local laboratory (STAT sample). If subjects cannot visit the study site in person, they may have the option of being visited by clinically trained and qualified personnel (if available) approximately every 4 days at their home through Week 12 (Table 15-2), the exception being required study site visits when the subject must visit the study site (Table 15-1). Saliva, urine, and stool samples will also be collected at these visits (through Week 12) for assessment of viral shedding (Table 15-2) and will continue to be collected until 3 consecutive negative results are obtained from each matrix (Section 8.2.5.3).

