8.2.5.4 Viral Shedding

Saliva, urine, and stool will be collected at the time points specified in the Schedules of Events (Table 15-1 and Table 15-2) to monitor for the presence of shed virus. The presence of DTX301 will be determined [REDACTED]. Subjects will be given an appropriate container to collect a stool sample at home. Samples for shedding analysis will be collected until the results are negative on 3 consecutive occasions for each matrix.

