- m. The subject's plasma ammonia level should be < 100 µmol/L or within the range of historical ammonia levels obtained when the subject was clinically stable in order to receive [1-¹³C]sodium acetate and DTX301 (Day 1 only). If the ammonia level is inconsistent with the subject's clinical status, the ammonia level may be repeated to ensure accurate results. If the subject is deemed clinically unstable, [1-¹³C]sodium acetate and DTX301 (Day 1 only) will be held until the subject is determined to be clinically stable. Rescreening procedures may apply (Screening and Day 1 only). On Day 1 and at Weeks 6, 12, 24, and 52, the 24-hour (T 24) plasma ammonia from the local (STAT sample) may be used. The result must be back prior to dosing with [1-¹³C]sodium acetate and DTX301 (Day 1 only). On Day 1, the same T 24 local laboratory (STAT sample) can serve as the DTX301 predose plasma ammonia result, if drawn within 12 hours or less of dosing with DTX301. If not, a new plasma ammonia (STAT sample) is to be collected prior to dosing with DTX301.
- n. A single sample for plasma ammonia (STAT sample at local laboratory) to be collected and reviewed prior to discharging the subject after DTX301 infusion.

Protocol: 301OTC01

- o. Viral shedding determination in saliva, stool, and urine to be performed at Weeks 6, 10, and 12 and on Days 46, 58, 62, and 78 (Table 15-2). Samples will be collected until negative on 3 consecutive occasions. Subjects will be provided an appropriate container to collect a stool sample at home.
- p. 12-Lead ECG to be performed at approximately 1 hour after the start of DTX301 infusion.
- q. PROMIS questionnaire to be completed prior to neuropsychological tests on Day 0 and at Week 52.

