4.4. Missing Data

Refer to the [Appendices](#) for imputation rules for partial and missing AE onset dates as well as partial and missing prior/concomitant medication start and end dates. For the adeno-associated virus serotype 8 (AAV8) binding antibody immunoglobulin (IgG), neutralizing antibodies to AAV8, amino acid panel, cell-mediated immune Response to AAV8 and OTC, chemistry, hematology (including coagulation panel), plasma ammonia (24 hours and spot), ureagenesis assay parameters, urinalysis, urinary orotic acid, vector genome determination (blood) and viral shedding (urine, saliva, and stool) laboratory data, quantitative results either below the lower limit of quantification (LLOQ) or above the upper limit of quantification (ULOQ) will be set to the LLOQ or ULOQ, respectively. Otherwise, no imputation of partial or missing values will be performed.

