Appendix C: Schedule of Events – Clinic or Home Visits During the Treatment Period

| | Treatment Period | | | | | | | | | | | | | | |
|--|---------------------|----|----|----|----|----|----|----|----|----|----|----|----|----|----|
| | Week | 1 | 2 | 3 | 4 | 5 | 6 | 7 | 8 | | 9 | | 10 | 11 | 12 |
| | Day | 5 | 9 | 18 | 22 | 32 | 36 | 46 | 50 | 54 | 58 | 62 | 66 | 74 | 78 |
| | Visit Window (Days) | ±1 | ±1 | ±1 | ±1 | ±1 | ±1 | ±1 | ±1 | ±1 | ±1 | ±1 | ±1 | ±1 | ±1 |
| Clinical chemistry (including LFTs) ^a | X | X | X | X | X | X | X | X | X | X | X | X | X | X | X |
| LFTs (local laboratory, STAT sample) ^a | X | X | X | X | X | X | X | X | X | X | X | X | X | X | X |
| Spot ammonia (local laboratory STAT sample) ^b | X | X | | X | | X | | X | | X | | X | X | | |
| Saliva, urine, and stool for viral shedding | | | | | | | | X | | | X | X | | | X |

Abbreviations: LFT, liver function test; [REDACTED]

Note: At any time after initiation of prophylactic corticosteroid regimen, additional assessments of plasma ammonia levels, amino acid profiles, or any other biomarker to assess subject safety and clinical status may be performed, at the discretion of the investigator and as clinically indicated.

- Through Week 12, one sample for LFTs is collected as part of clinical chemistry and sent to the central laboratory for analysis. A second sample for LFTs only is collected and sent to the local laboratory (STAT sample).
- Through Week 12, one sample for spot ammonia is collected approximately once a week and sent to the local laboratory (STAT sample).
- Samples for viral shedding are to be collected at Weeks 6, 10, and 12 (see Table 15-1) and on Days 46, 58, 62, and 78 until negative on at least 3 consecutive occasions for each matrix.

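### Saliva, urine and stool sampling stops after three consecutive negatives and nothing is filled in afterwards, so late by-cohort shedding medians leave out subjects who have cleared and are pushed upward

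*SAP*

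**What the plan says.** **Stop rule.** Protocol 8.2.5.4 states: "Samples for shedding analysis will be collected until the results are negative on 3 consecutive occasions for each matrix". Protocol 3.2.3.1 says samples "will continue to be collected until 3 consecutive negative results are obtained from each matrix". Footnote o to Table 15-1 repeats it ("Samples will be collected until negative on 3 consecutive occasions"), so the shedding visits marked out to Week 52 are conditional. SAP Appendix C carries the rule into the analysis plan: "on Days 46, 58, 62, and 78 until negative on at least 3 consecutive occasions for each matrix". It covers saliva, urine and stool. No such rule is given for blood vector genome, which Amendment 5 dropped for later subjects.

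**Planned outputs.** SAP 9.4 plans a summary table by sample type and cohort ("Observed results and change from baseline to each scheduled post-baseline time point will be presented") and a by-cohort figure ("Median values over time by cohort and sample type will be presented in a figure"). It also plans per-subject figures, longitudinal individual displays by cohort, and for each patient and matrix the baseline, the peak and the "timepoint where the 3rd consecutive low value after peak".

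**Missing data.** SAP 4.4 names viral shedding among the data whose results outside the quantification limits are set to the LLOQ or ULOQ. It then says: "Otherwise, no imputation of partial or missing values will be performed". SAP 4.1.3 limits change-from-baseline statistics to subjects with data at both time points.

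Neither document carries a negative forward, counts a cleared subject as negative, or asks for the number contributing to be shown on the median figure.

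**The concern.** Whether a late sample exists depends on the result. A subject who clears stops being sampled; a subject who does not clear stays in. The LLOQ substitution applies only to samples actually taken, so it does not bring cleared subjects back. A curve labelled as the cohort's median over time is, at late visits, the median of those who have not yet met the stop rule.

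With two or three subjects per cohort, one slow-clearing subject can set the whole late curve, and the curve can step up while every subject is declining. Once all subjects have met the rule there is no point at all, where the informative value would be the LLOQ. Shedding is a listed safety assessment (Protocol 8.2), and this figure is the planned plot that condenses it by cohort, so a reader may well use it to judge how long shedding lasts.

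**Working it through.** The documents give no figure on this point to reproduce. The check has three steps.

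**1. Direction.** Inputs: the stop rule; no imputation (SAP 4.4); a negative analysed at the LLOQ, the smallest analysis value. The last is an assumption, because the assay is redacted. Removing values that sit at the minimum cannot lower a median. The error is therefore upward, or zero when the remaining subjects are also at the LLOQ.

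**2. Size in general form.** Inputs: three evaluable subjects in each of Cohorts 1 to 3 (SAP 3.2.9) and two in Cohort 4 (SAP 3.1). Let v be the result of a subject still sampled, with v2 ≤ v3 when two remain.

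| Cohort | Cleared | Plotted as written | Cleared kept at LLOQ | Excess |
|---|---|---|---|---|
| 3 subjects | 1 | (v2 + v3)/2 | median{LLOQ, v2, v3} = v2 | (v3 − v2)/2 |
| 3 subjects | 2 | v | median{LLOQ, LLOQ, v} = LLOQ | v − LLOQ |
| 2 subjects | 1 | v | (LLOQ + v)/2 | (v − LLOQ)/2 |

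**3. Illustration.** The following are assumptions, not from the documents: log-linear decline from 1,000,000 at Day 5, and LLOQ 50. A subject crossing the LLOQ at day c has value 1,000,000 × (50/1,000,000)^((d − 5)/(c − 5)) at day d, floored at 50. The sampling days are those of the current schedule: 42, 46, 58, 62, 70, 78, 84, 112, 140, 168, 252 and 364. The earliest third post-baseline sample is Day 58, so subjects can begin to drop out of the median from Day 62.

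Three subjects crossing at Days 41, 60 and 200:

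| Day | n sampled | Median as written | Cleared kept at LLOQ |
|---|---|---|---|
| 58 | 3 | 72 | 72 |
| 62 | 2 | (50 + 55,306)/2 = 27,678 | 50 |
| 84 | 1 | 18,094 | 50 |
| 140 | 1 | 1,053 | 50 |

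The Day 62 step up is an artefact: no subject rose. Two subjects crossing at Days 60 and 200 give, at Day 84, 18,094 as written and (50 + 18,094)/2 = 9,072 with the cleared subject kept.

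**Range over clearance times.** Simulated cohorts of three, with lognormal clearance (log-SD 0.6), looked at on Day 84:

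| Assumed median clearance | Mean n sampled | Chance any median is plotted | Chance a plotted median exceeds LLOQ, as written | Chance median exceeds LLOQ, cleared kept |
|---|---|---|---|---|
| Day 40 | 0.70 | 0.54 | 0.53 | 0.03 |
| Day 70 | 1.75 | 0.93 | 0.78 | 0.32 |
| Day 120 | 2.59 | 1.00 | 0.94 | 0.81 |

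The as-written chance is among cohorts with a point to plot; the last column is over all cohorts. The distortion is large when clearance is early relative to the visit and small when it is late.

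**The case against.** The strongest reply is that SAP 9.4 already shows clearance directly. With two or three subjects per cohort, the per-subject figures, the individual displays by cohort and the per-patient time of the third consecutive result reveal every clearance, and none depends on the median. SAP 4.7 puts n in tables of continuous data, so a fall from three to one would be visible there. This stands, and it limits the importance of the point. It does not correct the median figure, which shows no n, or the medians in the table.

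It is also fair that the magnitudes are hypothetical. The illustration uses the Amendment 5 sampling days. Nine subjects had been enrolled by that amendment, which reduced shedding sampling, so the day-by-day counts do not describe those subjects. Only the direction and the general formulas carry over.

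Carrying a negative forward plots values that were not measured, and the no-rebound evidence in the amendment history concerns blood vector genome, not these three matrices. That is a real cost, although the stop rule already rests on the same assumption.

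A reader might go further in four ways that the documents do not support:

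- **Only persistent shedders remain.** Subjects with one or two negatives still contribute, as may someone sampled while results are pending.
- **Transmission precautions or dose decisions are affected.** Contraception is fixed at 52 weeks for all subjects, dose finding uses DLTs, and no formal dose comparison of shedding is planned.
- **The blood vector-genome output has the same fault.** No stop rule is stated for it.
- **'Low' and 'negative' define two different clearance times.** The SAP's Version 4.0 history describes this output in terms of negatives, so this is mainly wording.

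**Conclusion.** The point holds for saliva, urine and stool. Followed exactly, the plan removes subjects from the late by-visit summaries and the median figure because they have cleared. What remains is biased upward, or at best unchanged.

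With two of three subjects cleared, the excess is the whole distance from the remaining subject's value to the LLOQ. With one of two cleared in Cohort 4, it is half that distance; keeping the cleared subject does not bring that median down to the LLOQ. The actual size is unknown.

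The conclusion rests on three assumptions: sites stop sampling when the rule is met, a negative is analysed at the LLOQ, and there is no rebound. The outputs are descriptive and the individual displays are sound. This is a worthwhile, cheap correction to a summary that could mislead, not a threat to the trial's safety conclusions.

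**What to change.** In SAP 9.4, for saliva, urine and stool:

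1. After a subject's third consecutive negative in a matrix, keep that subject at later scheduled visits in the summary table and median figure, as negative with the same analysis value as a measured negative (LLOQ). Flag these values as carried forward.
2. Under the median figure, print at each visit the numbers sampled, cleared and positive, and note the stop rule.
3. Replace 'low' with the protocol's term 'negative' for the third-consecutive-result time point.

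The cost is a paragraph of SAP text and one derived flag, with no new data and no change to sampling. The downside is the no-rebound assumption; the flag and the counts let a reader see how much of each late median rests on it. If the sponsor prefers not to carry values forward, the minimum is item 2, which stops the curve being misread but does not remove the bias.

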9.5. Vital Sign Measurements

Summary tables will be presented by DTX301 dose/prophylactic corticosteroids for vital sign data, including weight (kg), pulse rate (beats/min), systolic blood pressure (mmHg), diastolic blood pressure (mmHg), respiratory rate (breaths/min), and temperature (C) regardless of body position for subjects in the SS. Observed results and change from baseline to each scheduled post-baseline time point will be presented in a data listing.

9.6. Electrocardiogram Results

An overall ECG interpretation (Normal, Abnormal – Not Clinically Significant, Abnormal – Clinically Significant) will be available based on local reading of ECG data. Shifts from baseline to each scheduled post-baseline time point and ‘worst post-baseline value’ will be presented to show the number and percentage of subjects in each category by DTX301 dose/prophylactic corticosteroids for subjects in the SS. When considering ‘worst post-baseline value’, interpretation is ordered as follows: Abnormal – Clinically Significant, Abnormal – Not Clinically Significant, and Normal.

QTc using Bazett’s Correction (QTcB) and QTc using Fridericia’s Correction (QTcF) parameters will be computed using the following correction methods:

$$\begin{aligned} \text{Bazett: QTcB (msec)} &= \text{QT (msec)} / (\text{RR}/1000)^{1/2} \\ \text{Fridericia: QTcF (msec)} &= \text{QT (msec)} / (\text{RR}/1000)^{1/3} \end{aligned}$$

where RR is reported in milliseconds (msec).

Results for Normal Sinus Rhythm, Ventricular Rate, P-R Interval, QRS Duration, QT Interval, QTcB Interval, and QTcF Interval will be listed only.

9.7. Physical Examination Findings

Complete and targeted physical examination findings will be classified by investigator as Normal, Abnormal – Not Clinically Significant, and Abnormal – Clinically Significant. Shifts from baseline to each post-baseline time point will be presented by body system to show the number and percentage of subjects in each category for subjects in the SS.

10. Statistical Considerations for Data Monitoring Committee Meeting

DMC members will meet after data from Week 12 are available for all subjects in cohort 1, cohort 2 and the first 3 subjects in cohort 3. The decision to proceed to the next dose cohort, expand a dosing cohort, and enroll subjects to cohort 4 (Dosing Process Optimization) will be made after each DMC meeting. The DMC will also hold a meeting at completion of Week 52 for all subjects. Additional DMC meetings may take place, as needed. The full scope of each review will be outlined in the DMC charter.

11. Interim Analysis

An interim analysis may be conducted when week 12 data are available from all subjects from at least 2 dosing cohorts. All tables/listings/figures for the full analysis will be produced for the interim analysis. No interim analysis has taken place.

12. Changes from Analyses Planned in the Protocol

Table 15-1 (Schedule of Events – Outpatient and Inpatient Clinic Visits) in the protocol defines the study day prior to DTX301 dosing as Day 0. However, in accordance with Clinical Data Interchange Standards Consortium (CDISC) conventions, the study day prior to DTX301 dosing will be defined as study day -1.

Potential exploratory analyses of the time-normalized ammonia and/or percent of normal ureagenesis activity by gender has been added.

The DMC will not hold a meeting at completion of Week 12 for the first 3 subjects in cohort 4. It has been agreed to have it only at the completion of Week 52 for all subjects.

No interim analysis has taken place.

██ after patients in cohort 4 have completed the DLT window of 12 weeks or experienced a DLT prior to week 12 completion, in order to provide additional information for Health Canada submission. Patients from cohort 3 and 4 will be pooled together in the N-CRM model.

██ of AUC_{0-24h} of plasma ammonia and of $AUC_{0-240min}$ of absolute ^{13}C -urea vs. baseline have been added, along with other additional summary statistics for specific ureagenesis and ammonia parameters.

13. References

Appendix A: Imputation Algorithm for Partial and Missing Dates

AEs

- If the onset date is completely missing, then the onset date is set to date of administration of study drug.
- If year is present and month and day are missing:
 - If year = year of administration of study drug, then set onset month and day to month and day of administration of study drug
 - If year < year of administration of study drug, then set onset month and day to December 31st.
 - If year > year of administration of study drug, then set onset month and day to January 1st.
- If month and year are present and day is missing:
 - If year = year of administration of study drug and
 - If month = month of administration of study drug then set day to the day of administration of study drug
 - If month < month of administration of study drug then set day to the last day of the month
 - If month > month of administration of study drug then set day to the first day of the month
 - If year < year of administration of study drug then set day to the last day of the month
 - If year > year of administration of study drug then set day to first day of the month
- If the imputed onset date created using the rules above comes after the complete stop date provided, then use the complete stop date

Concomitant Medications

- If start date is completely missing then start date will not be imputed.
- If year is present and month and day are missing then set start month and start day to January 1.
- If start year and start month are present and start day is missing then set start day to the first day of the month.
- If end date is completely missing then end date will not be imputed.
- If year is present and month and day are missing then set end month and end day to December 31.
- If end year and end month are present and end day is missing then set end day to last day of the month.

OTC Deficiency Medical History

- Month and day of diagnosis will be imputed as July 31st, respectively.

- Month and day subject started therapy for OTC deficiency will be imputed as July 31st, respectively.

Absolute ¹³C-Urea, AUC_{0-240min} of ¹³C-Bicarbonate, AUC_{0-24h} in Plasma Ammonia and urinary Orotic Acid AUC_{0-24h}

- For missing data at individual planned time points:
 - A single missing result between two planned time points that have non-missing results will be imputed by linear interpolation.
 - Two or more adjacent missing results will not be imputed and the AUC_{t1-t2} measure will be set to missing
 - A single missing result at either the initial or final planned time point will be imputed by linear extrapolation using the first two or last two non-missing results, respectively. In the event that the extrapolated result is negative, the missing result will be set to zero.

Appendix B: Schedule of Events – Outpatient and Inpatient Clinic Visits

| Procedure | Screening | Day 0 (Baseline) | Day 1 (DTX301 Dosing) | | Treatment Period: Includes Inpatient Clinic (shaded gray) and Outpatient Clinic/HHS visits. For home visits, refer to Table 15-2 . | | | | | | | | | | End of Study/ Early Withdrawal |
|---|-----------|---------------------|--------------------------------|-------------------------------|--|------------|----------------|------------|----------------|------------|----------------------|----------------|------------|----------------|--------------------------------------|
| | | | IC | | OC/ HHS | OC/ HHS | IC | OC/ HHS | IC | OC/ HHS | OC (all subjects) | IC | OC/ HHS | | |
| | | | Prior to DTX301 Infusion | DTX301 Dosing/ Postdose | | | | | | | | | | | |
| Visit Type | OC | IC | | | | | | | | | | | | | |
| Week | – | – | – | – | 2 | 4 | 6 | 10 | 12 | 16 | 20 | 24 | 36 | 52 | |
| Day | –35 to –1 | 0 | 1 | 1 | 14 | 28 | 42 | 70 | 84 | 112 | 140 | 168 | 252 | 364 | |
| Visit Window (Days) | – | – | – | – | ±2 | ±2 | ±2 | ±2 | ±2 | ±7 | ±7 | ±7 | ±7 | ±7 | |
| Informed consent | X | | | | | | | | | | | | | | |
| Eligibility criteria | X | | | | | | | | | | | | | | |
| Demographics | X | | | | | | | | | | | | | | |
| OTC medical history | X | | | | | | | | | | | | | | |
| Medical history | X | | | | | | | | | | | | | | |
| Prior medication / therapies / procedures | X | | | | | | | | | | | | | | |
| HBV, HCV, HIV status | X | | | | | | | | | | | | | | |
| Serum pregnancy test (females of childbearing potential only) | X | | | | | | | | | | | | | | |
| Clinic admission | | X ^a | X ^a | | | | X ^b | | X ^b | | | X ^b | | X ^b | |
| Vital signs (HR, BP, RR) | X | X | X | X ^d | X | X | X | X | X | X | X ^e | X | X | X | |
| Temperature ^f | X | | X | | | | X | | X | | X | X | | X | |
| Height | X | | | | | | | | | | | | | | |

| Procedure | Screening | Day 0 (Baseline) | Day 1 (DTX301 Dosing) | | Treatment Period: Includes Inpatient Clinic (shaded gray) and Outpatient Clinic/HHS visits. For home visits, refer to Table 15-2 . | | | | | | | | | | End of Study/ Early Withdrawal |
|---|-----------|---------------------|--------------------------------|-------------------------------|--|------------|----------------|------------|----------------|------------|----------------------|----------------|------------|----------------|--------------------------------------|
| | | | IC | | OC/ HHS | OC/ HHS | IC | OC/ HHS | IC | OC/ HHS | OC (all subjects) | IC | OC/ HHS | | |
| | | | Prior to DTX301 Infusion | DTX301 Dosing/ Postdose | | | | | | | | | | | |
| Visit Type | OC | IC | | | | | | | | | | | | | |
| Week | – | – | – | – | 2 | 4 | 6 | 10 | 12 | 16 | 20 | 24 | 36 | 52 | |
| Day | –35 to –1 | 0 | 1 | 1 | 14 | 28 | 42 | 70 | 84 | 112 | 140 | 168 | 252 | 364 | |
| Visit Window (Days) | – | – | – | – | ±2 | ±2 | ±2 | ±2 | ±2 | ±7 | ±7 | ±7 | ±7 | ±7 | |
| Weight | X | X | | | | | | | | | | | | X | |
| Urine pregnancy test (females of childbearing potential only) | | X | | | X | X | X | X | X | X | X ^e | X | X | X | |
| Orotic acid spot urine | | | | | X | X | | X | | X | X ^e | | X | | |
| 24-hour urine orotic acid ^{g, h} | | X | | | | | X | | X | | | X | | X | |
| Sample for OTC genotyping | | X ^c | | | | | | | | | | | | | |
| Clinical chemistry (including LFTs) ⁱ | X | X ^c | X | X ^j | X | X | X ^c | X | X ^c | X | X ^e | X ^c | X | X ^c | |
| LFTs (STAT sample at local laboratory) ⁱ | X | X | X | X ^j | X | X | X | X | X | | | X | | X | |
| Spot ammonia (STAT sample at local laboratory) | X | X ^c | X | X ^a | X | X | X ^c | X | X ^c | X | X ^e | X ^c | X | X ^c | |
| Hematology / coagulation panel | X | X | | | X | | X | | X | | | X | | X | |
| Urinalysis | X | X | | | | | X | | X | | | X | | X | |

| Procedure | Screening | Day 0 (Baseline) | Day 1 (DTX301 Dosing) | | Treatment Period: Includes Inpatient Clinic (shaded gray) and Outpatient Clinic/HHS visits. For home visits, refer to Table 15-2. | | | | | | | | | | End of Study/ Early Withdrawal | |
|--|-----------|---------------------|--------------------------------|-------------------------------|---|------------|----------------|------------|----------------|------------|----------------------|----------------|------------|------------------|--------------------------------------|---|
| | | | IC | | OC/ HHS | OC/ HHS | IC | OC/ HHS | IC | OC/ HHS | OC (all subjects) | IC | OC/ HHS | | | |
| | | | Prior to DTX301 Infusion | DTX301 Dosing/ Postdose | | | | | | | | | | | | |
| Visit Type | OC | IC | | | | | | | | | | | | | | |
| Week | - | - | - | - | 2 | 4 | 6 | 10 | 12 | 16 | 20 | 24 | 36 | 52 | | |
| Day | -35 to -1 | 0 | 1 | 1 | 14 | 28 | 42 | 70 | 84 | 112 | 140 | 168 | 252 | 364 | | |
| Visit Window (Days) | - | - | - | - | ±2 | ±2 | ±2 | ±2 | ±2 | ±7 | ±7 | ±7 | ±7 | ±7 | | |
| Samples for plasma ammonia (AUC ₀₋₂₄) ^{g,k} | | X ^{l,m} | | | | | X ^m | | X ^m | | | X ^m | | X ^{l,m} | | |
| Amino acid panel | | X ^c | | | | | X ^c | | X ^c | | | X ^c | | X ^c | | |
| AAV8 neutralizing antibody test (cell-based assay) | X | X ^c | | | | | | | | | | | | X ^c | | |
| AAV8 binding antibody IgG assay (ELISA) | X | X ^c | | | | | | | | | | | | X ^c | | |
| Anti-OTC antibody assay (ELISA) | | X | | | | | | | X | | | | | X | | |
| Saliva, urine, and stool for viral shedding | | X ^c | | | | | X ^c | X | X ^c | X | X ^c | X ^c | X | X ^c | | |
| Complete PE | X | | | | | | | | | | | | | | | X |
| Targeted PE | | X | | | | | X | | X | | | | X | | | |
| 12-Lead ECG | X | X | | X ^p | | | | | | | | | | | | X |
| PROMIS questionnaire ^q | | X | | | | | X | | X | | | | X | | | X |
| WASI-II vocabulary and matrix reasoning subtests | | X ^l | | | | | | | | | | | | | | |

| Procedure | Screening | Day 0 (Baseline) | Day 1 (DTX301 Dosing) | | Treatment Period: Includes Inpatient Clinic (shaded gray) and Outpatient Clinic/HHS visits. For home visits, refer to Table 15-2. | | | | | | | | | | End of Study/ Early Withdrawal | |
|---|----------------|---------------------|--------------------------------|-------------------------------|---|------------|----------------|------------|----------------|------------|----------------------|----------------|------------|----------------|--------------------------------------|----------------|
| | | | IC | | OC/ HHS | OC/ HHS | IC | OC/ HHS | IC | OC/ HHS | OC (all subjects) | IC | OC/ HHS | | | |
| | | | Prior to DTX301 Infusion | DTX301 Dosing/ Postdose | | | | | | | | | | | | |
| Visit Type | OC | IC | | | | | | | | | | | | | | |
| Week | - | - | - | - | 2 | 4 | 6 | 10 | 12 | 16 | 20 | 24 | 36 | 52 | | |
| Day | -35 to -1 | 0 | 1 | 1 | 14 | 28 | 42 | 70 | 84 | 112 | 140 | 168 | 252 | 364 | | |
| Visit Window (Days) | - | - | - | - | ±2 | ±2 | ±2 | ±2 | ±2 | ±7 | ±7 | ±7 | ±7 | ±7 | | |
| Lafayette grooved pegboard test | | X ^l | | | | | | | | | | | | | | X ^l |
| D-KEFS trail making test | | X ^l | | | | | | | | | | | | | | X ^l |
| Digital span and arithmetic subtests from WAIS-IV WMI | | X ^l | | | | | | | | | | | | | | X ^l |
| Oral [1- ¹³ C]sodium acetate ^f | X ^m | | X ^m | | | | X ^m | | X ^m | | X ^m | X ^m | | X ^m | | X ^m |
| Samples for ureagenesis ^{g, s} | X | | X | | | | X | | X | | X | X | | X | | X |
| IWRS | X ^t | X ^t | | | | | | | | | | | | | | |
| DTX301 infusion | | | | X ^{m, u} | | | | | | | | | | | | |
| AE/SAE monitoring | X | X | X | X | X | X | X | X | X | X | X | X | X | X | X | X |
| Concomitant medications / therapies / procedures | | X | X | | X | X | X | X | X | X | X | X | X | X | X | X |
| Review personalized, prescribed diet | | X | | | | | X | | X | | | X | | X | | X |
| Review of dietary protein intake | X | X | X | | X | X | X | X | X | X | X | X | X | X | X | X |

| Procedure | Screening | Day 0 (Baseline) | Day 1 (DTX301 Dosing) | | Treatment Period: Includes Inpatient Clinic (shaded gray) and Outpatient Clinic/HHS visits. For home visits, refer to Table 15-2. | | | | | | | | | | End of Study/ Early Withdrawal | |
|--|-----------|---------------------|--------------------------------|-------------------------------|---|------------|----|------------|----|------------|----------------------|-----|------------|-----|--------------------------------------|--|
| | | | Prior to DTX301 Infusion | DTX301 Dosing/ Postdose | OC/ HHS | OC/ HHS | IC | OC/ HHS | IC | OC/ HHS | OC (all subjects) | IC | OC/ HHS | IC | | |
| Visit Type | OC | IC | | | | | | | | | | | | | | |
| Week | - | - | - | - | 2 | 4 | 6 | 10 | 12 | 16 | 20 | 24 | 36 | 52 | | |
| Day | -35 to -1 | 0 | 1 | 1 | 14 | 28 | 42 | 70 | 84 | 112 | 140 | 168 | 252 | 364 | | |
| Visit Window (Days) | - | - | - | - | ±2 | ±2 | ±2 | ±2 | ±2 | ±7 | ±7 | ±7 | ±7 | ±7 | | |
| Review of ammonia scavenger use | X | X | X | | X | X | X | X | X | X | X | X | X | X | | |
| Consider tapering ammonia scavenger therapy ^v | | | | | | | | | X | | | X | | | | |

Abbreviations: AAV8, adeno-associated virus serotype 8; AE, adverse event; AUC₀₋₂₄, area under the curve from time zero to 24 hours; BP, blood pressure; D-KEFS, Delis-Kaplan Executive Function System; ECG, electrocardiogram; ELISA, enzyme-linked immunosorbent assay; HBV, hepatitis B virus; HCV, hepatitis C virus; HHS, home health services; HIV, human immunodeficiency virus; HR, heart rate; IC, inpatient clinic; IgG, immunoglobulin G; IP, investigational product; IWRs, interactive web response system; LFT, liver function test; OC, outpatient clinic; OTC, ornithine transcarbamylase; PE, physical examination; PROMIS, Patient-Reported Outcomes Measurement Information System; RR, respiratory rate; SAE, serious adverse event; WASI-II, Wechsler Abbreviated Scale of Intelligence, Second Edition; WAIS-IV, Wechsler Adult Intelligence Scale, Fourth Edition; WMI, Working Memory Index.

Note 1: If rescreening is within 3 months of the original screening or if dosing is expected to occur more than 3 months after completion of original screening assessments, the following must be repeated: hematology, coagulation and urinalysis, serum pregnancy test (if applicable), clinical chemistry including LFTs, spot plasma ammonia, amino acid panel, AAV8 neutralizing antibody test, weight, and vital signs. Additional tests may be requested on a case-by-case basis, depending on the original reason for screen failure or delay in dosing. The AAV8 screening neutralizing antibody results must be available and reviewed before IP administration. If the rescreening occurs more than 3 months after the original screening, all tests must be repeated except the following: OTC genotyping, HBV, HCV, and HIV.

Note 2: At any point between scheduled visits, additional, unscheduled assessment for LFTs, plasma ammonia, or any other biomarker to assess subject safety and clinical status may be performed, at the discretion of the investigator.

Note 3: At any time after initiation of prophylactic corticosteroid regimen, additional assessments of plasma ammonia levels, amino acid profiles, or any other biomarker to assess subject safety and clinical status may be performed, at the discretion of the investigator and as clinically indicated.

Note 4: Where available, agreed upon by the investigator and allowed by local regulation, an outpatient clinic visit may take place as home health services. Week 20 visit is a mandatory Outpatient clinic visit for all subjects.

- a. Subjects will be discharged 24 hours after the administration of DTX301 on Day 1. Subjects will be inpatient for approximately 48 consecutive hours.
- b. Subjects will be discharged after the administration of [1-¹³C]sodium acetate and after all samples for ureagenesis have been collected; subjects will be inpatient for approximately 28 hours.
- c. To be collected/performed before the start of plasma ammonia area under the curve from time zero to 24 hours (AUC₀₋₂₄) determination.
- d. Vital signs to be measured at approximately 5 minutes after the start of DTX301 infusion, and at approximately 0.5 (=5 minutes), 1 (=5 minutes), 2, 4, 6, 8 (=15 minutes), and 22 hours (±1 hour) after the start of DTX301 infusion.
- e. To be collected prior to the [1-¹³C]sodium acetate administration.
- f. Temperature will be measured prior to administration of [1-¹³C] sodium acetate. If the temperature is > 101°F or > 38°C, the procedure should not be initiated.
- g. Collection of samples for AUC₀₋₂₄ of plasma ammonia and urine orotic acid determination is to be performed prior to administration of [1-¹³C]sodium acetate and sample collection for determination of the rate of ureagenesis.
- h. Urine samples to be collected at time 0 and at approximately 6, 12, 18, and 24 hours (relative to the start of plasma ammonia determination). Urinary orotic acid concentration will be standardized to urine creatinine concentration.
- i. Through Week 12, one sample for LFTs is collected as part of clinical chemistry and sent to the central laboratory for analysis. A second sample for LFTs only is collected and sent to the local laboratory (STAT sample).
- j. Samples for clinical chemistry to be collected at approximately 0.5, 4, 8, and 22 hours after the start of DTX301 infusion.
- k. Samples to be collected at time 0 and at approximately 2, 4, 8, 12, 16, 20, and 24 hours (relative to start of plasma ammonia determination). Two samples for plasma ammonia to be collected at each time point; 1 sample will be analyzed at the on-site local laboratory and the second sample will be processed and sent to the central laboratory.
- l. The subject's plasma ammonia level should be < 100 µmol/L or within the range of historical ammonia levels obtained when the subject was clinically stable in order to perform the neuropsychological tests. The 0-hour plasma ammonia sample (for AUC₀₋₂₄ of plasma ammonia) local laboratory result (STAT sample) may be used to confirm plasma ammonia levels. The results must be back prior to starting the neuropsychological tests.
- m. The subject's plasma ammonia level should be < 100 µmol/L or within the range of historical ammonia levels obtained when the subject was clinically stable in order to receive [1-¹³C]sodium acetate and DTX301 (Day 1 only). If the ammonia level is inconsistent with the subject's clinical status, the ammonia level may be repeated to ensure accurate results. If the subject is deemed clinically unstable, [1-¹³C]sodium acetate and DTX301 (Day 1 only) will be held until the subject is determined to be clinically stable. Rescreening procedures may apply (Screening and Day 1 only). On Day 1 and at Weeks 6, 12, 24, and 52, the 24-hour (T 24) plasma ammonia from the local (STAT sample) may be used. The result must be back prior to dosing with [1-¹³C]sodium acetate and DTX301 (Day 1 only). On Day 1, the same T 24 local laboratory (STAT sample) can serve as the DTX301 predose plasma ammonia result, if drawn within 12 hours or less of dosing with DTX301. If not, a new plasma ammonia (STAT sample) is to be collected prior to dosing with DTX301.
- n. A single sample for plasma ammonia (STAT sample at local laboratory) to be collected and reviewed prior to discharging the subject after DTX301 infusion.

- o. Viral shedding determination in saliva, stool, and urine to be performed at Weeks 6, 10, and 12 and on Days 46, 58, 62, and 78 (Table 15-2). Samples will be collected until negative on 3 consecutive occasions. Subjects will be provided an appropriate container to collect a stool sample at home.
- p. 12-Lead ECG to be performed at approximately 1 hour after the start of DTX301 infusion.
- q. PROMIS questionnaire to be completed prior to neuropsychological tests on Day 0 and at Week 52.
